## **8. Data Collection and Data Monitoring**

Prior to any work being performed on this research proposal it will be submitted for review and approval by the Institutional Review Board at JHU. We will maintain a master list of patients with unique study identifiers. The master list will be maintained on a password protected computer or institutional network drive. Data will be entered into a database that will be stored on a secure server at the Johns Hopkins University. All research staff will be instructed as to how to maintain the highest ethical standards in protocol adherence and data collection. Standard backup procedures are in place at the institution to prevent catastrophic loss of data. Validity and accuracy checks will be put in place as data are entered into the database using preset field choices where applicable. Edits of the data will be performed routinely to look for missing data, outliers, unusual or inconsistent values. We will collect information on all neonates and parents enrolled in the study.

**For parents**, using standard questions that will be incorporated into the case report form, we will collect their date of birth, race, ethnicity, gender, educational level, underlying medical conditions (especially skin diseases that predispose to *S. aureus* colonization), current medications, exposure to recent antibiotics, recent healthcare exposures, other household members, past use of mupirocin, and dates of, and treatments for any prior *S. aureus* infections.

**For neonates**, we will collect basic demographic information on all patients, including chronologic age (date of birth), birth weight, mode of delivery, gestational age, race, ethnicity, gender, antimicrobials (antibiotics, antifungals, antivirals) administered, other interventional or clinical medicines that may impact *S. aureus* colonization, presence of central venous catheter, respiratory support, feeding method (breastfeeding, orogastric tube, nasogastric tube), dates of NICU admission and discharge, primary reason for admission (primary condition), where neonate was admitted from (home, other hospital, inborn), procedures, number of trips to the operating room or radiology, on NP or resident service, number of consulting teams, APGAR scores, practice and timing of kangaroo care, days in isolette vs. open crib or bed, dates and results of all *S. aureus* surveillance cultures and other cultures sent during routine clinical care.

### **Compliance with Hand Hygiene**

The JHH and JHBMC Departments of Hospital Epidemiology and Infection Control monitor compliance with hand hygiene on a monthly basis. We will have access to these data.

### **Adverse events collection and reporting**

As described above, participants on treatment will be instructed to report any rash, blister, itching, redness, swelling or other skin irritation, swelling of the face or limbs, difficulty breathing or swallowing, and any significant discomfort or illness that occurs during treatment. Study staff will specifically ask for these symptoms every day while monitoring compliance with treatment and will report any adverse event that is thought to be related to the study on the Adverse Event Log as well as any other perceived adverse events. Neonates will be monitored for Serious Adverse Events.

### **Adverse Event Definitions -**

**Adverse Event (AE):** An adverse event will be defined as an unusual and undesirable symptom or sign that occurs in parent participants during the clinical study. Adverse events include those clinically significant laboratory values and test results, concomitant illness, accident, medical occurrence or worsening of existing medical condition that emerge during study participation.

**Serious Adverse Event (SAE):** A Serious AE is any untoward medical occurrence that at any dose produces any of the following outcomes in neonate and parent participants:

- Results in death;
- Is life threatening (defined as an event in which the subject was at risk of death at the time of the event; it does not refer to an event which hypothetically might have caused death if it were more severe);
- Requires inpatient hospitalization or causes prolongation of existing hospitalization (see NOTE below for exceptions);
- Results in persistent or significant disability/incapacity;
- Is a congenital anomaly/birth defect (note: reports of congenital anomalies/birth defects must also be reported on the Pregnancy Supplemental Form);
- Is an important medical event (defined as a medical event(s) that may not be immediately life threatening or result in death or hospitalization but, based upon appropriate medical and scientific judgment, may jeopardize the subject or may require intervention [e.g., medical, surgical] to prevent one of the other serious outcomes listed in the definition above). Examples of such events include, but are not limited to, intensive treatment in an emergency room or at home for allergic bronchospasm; blood dyscrasias or convulsions that do not result in hospitalization.)

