### **B. Rationale**

Up to 40% of neonates acquire *S. aureus* in the first two months of life. Vertical transmission of *S. aureus* is rare, but postnatal transmission from mother to healthy infants is common in the first few months of life. Although healthcare workers have been implicated as a source of spreading *S. aureus* in NICUs, they are often not the source for transmission of *S. aureus* in NICUs. In addition to HCWs, parents have been identified as sources of *S. aureus* transmission.

Our preliminary data suggest that the majority of MRSA strains acquired by neonates in our NICU were not acquired from healthcare workers, so parents, rather than healthcare workers, may be the key reservoirs from which neonates acquire *S. aureus* colonization in the NICU. This finding is consistent with a changing NICU environment where skin-to-skin contact between parents and neonates is encouraged and may promote *S. aureus* transmission, while common hospital infection prevention measures have reduced healthcare worker transmission of *S. aureus*. We will test whether detection and treatment of *S. aureus* colonized parents with intranasal mupirocin and topical chlorhexidine bathing will decrease the risk of their infant acquiring *S. aureus* in the NICU. Reducing *S. aureus* burden has been shown to decrease infections. Rather than a patient-directed approach (screening and treating *S. aureus* colonized neonates) which has major limitations in the neonatal population, we propose a parent-directed approach that eliminates or delays a neonate's exposure. Similar to vaccinating pregnant mothers with influenza vaccine to prevent disease in newborn infants, we propose to engage parents in preventing HAIs in their children.

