## B. Intervention

Subjects (parents of neonates) will receive an ointment and cloths with standardized instructions for use. The instructions will be the same for all subjects. Approximately 1 cm ribbon of ointment will be self-administered by inserting a new cotton-tipped applicator into each anterior nares. A new cotton-tipped applicator will be used for each nares followed by gentle massaging of the nares to ensure distribution of the ointment. This procedure will be performed twice daily for five days. Verbal and printed instructions will be provided to parents. Study staff will demonstrate application of mupirocin ointment to the anterior nares. Parents will self-administer all doses of the intervention. Subjects will also be given pre-packaged cloths for daily skin cleaning. Each package contains 6 cloths. Each cloth will be used to wipe a designated body area (arms, legs, chest and neck, back and perineum) once a day for 5 days. Study staff will demonstrate how to apply CHG to the skin and instruct parents to not rinse after using the cloths. Participants will be instructed to perform the baths on the same 5 days they apply the intranasal ointment.

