**Mupirocin Ointment Possible Adverse Effects:** Local adverse effects may be associated with mupirocin application. Mupirocin ointment may cause itching, pain, stinging, and burning. Local effects from the nasal formulation have included epistaxis, rhinitis, taste perversion, pharyngitis, burning, and cough. Gastrointestinal side effects have included nausea (1.1%), abdominal pain (<1%), and diarrhea (<1%). Dry mouth has been reported with mupirocin nasal (<1%). Nervous system side effects associated with intranasal mupirocin have included headache (9%). Dizziness has been reported with mupirocin ointment (<1%). Ocular side effects associated with mupirocin nasal ointment have included blepharitis (<1%).

**Chlorhexidine Gluconate-impregnated Cloths Possible Adverse Effects:** The soap may cause burning and dryness of the skin. It may cause burning of the eyes, but it's not recommended to be used above the neck. Skin erythema and roughness, dryness,

sensitization, allergic reactions are possible, but rare.

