**NOTE: For the purposes of this trial, the following hospitalizations will not be considered SAEs:**

- Admissions as per protocol for a planned medical/surgical procedure;
- Routine health assessment requiring admission for baseline/trending of health status (e.g. post-partum complications, such as wound infection or bleeding);
- Medical/surgical admission for purposes other than remedying ill health state and was planned prior to entry into the study. Appropriate documentation is required in these cases;

- Admission encountered for another life circumstance that carries no bearing on health status and requires no medical/surgical intervention (e.g., lack of housing, economic inadequacy, care-giver respite, family circumstances, administrative).

**Non-Serious Adverse Event:** A non-serious adverse event is any adverse event not classified as serious. All non-serious AEs will be reported to the IRB on an annual basis with the continuing review.

**Adverse Event Grading:** The Division of AIDS Table of Grading Severity of Adult and Pediatric Adverse Experiences (DAIDS) Version 2 will be used to assess severity and provide the grade for each AE that is reported. The investigator will evaluate the severity of any adverse event not identified within the below criteria using the following definitions:

- **Mild (Grade 1)**- Mild symptoms causing no or minimal interference with usual social & functional activities with intervention not indicated
- **Moderate (Grade 2)**- Moderate symptoms causing greater than minimal interference with usual social & functional activities with intervention indicated
- **Severe (Grade 3)** - Severe symptoms causing inability to perform usual social & functional activities with intervention or hospitalization indicated
- **Potentially life threatening (Grade 4)** - symptoms causing inability to perform basic self-care functions with intervention indicated to prevent permanent impairment, persistent disability.
- **Death (Grade 5)**: Indicates death.

AEs graded as Grade 3 or higher which are possibly, probably, or definitely attributable to the use of the investigational drug will be recorded and monitored until the event has resolved to meet the definition of 'mild'.

All adverse events will be further evaluated for attribution as per the following:

- **Unrelated**: Adverse event is clearly not related to the investigational agent
- **Unlikely**: Adverse event is doubtfully related to the investigational agent

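### Section 8 defines adverse events in parents only and monitors neonates only for serious events, so mild or moderate neonatal skin reactions are not defined, solicited or compared by arm

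*Combined protocol and SAP*

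**What the plan says.** **Definitions (Section 8, Adverse Event Definitions).** The adverse event definition names one population: "An adverse event will be defined as an unusual and undesirable symptom or sign that occurs in parent participants during the clinical study". The serious adverse event definition that follows names two: "any untoward medical occurrence that at any dose produces any of the following outcomes in neonate and parent participants". The non-serious category is derived from the first: "A non-serious adverse event is any adverse event not classified as serious".

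**Collection (Section 8, Adverse events collection and reporting; Section 5.B, outcome 5).** Staff ask participants on treatment, who are the parents, about listed symptoms daily during the course and at Day 6. The log also has room for other events perceived as adverse. For infants the instruction is: "Neonates will be monitored for Serious Adverse Events".

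**Analysis (Section 9.C).** Adverse events as Section 8 defines them are reported overall and by arm, and compared with Fisher's exact test.

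**Exposure (Sections 2.B, 4.B and 8).** Parents use the cloths to "wipe a designated body area (arms, legs, chest and neck, back and perineum) once a day for 5 days", and staff "instruct parents to not rinse after using the cloths". The rationale describes a NICU in which "skin-to-skin contact between parents and neonates is encouraged". The neonatal data list in Section 8 includes the practice and timing of kangaroo care. It has no item for skin reactions.

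**Known effects (Section 6.A).** Besides erythema, roughness and dryness, the protocol says of the chlorhexidine cloths: "sensitization, allergic reactions are possible, but rare". It does not discuss product passing from parent to infant.

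**The concern.** The trial rests on the idea that close contact carries *S. aureus* from parent to infant. The same contact is a plausible route for product left on the parent's skin. The infants include a randomization stratum below 1500 g, and they are the group the intervention is meant to protect. Yet the plan sets out systematic collection of non-serious reactions only for the treated adults.

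At stake is what the trial can say about local tolerability in infants. If the intervention works, units considering it will ask whether infants' skin was affected. The trial has a masked placebo arm and regular contact with every family, so it is well placed to give a descriptive answer. As written, it will not have the data in a form that can be reported by arm.

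**Working it through.** The plan states no figure on this point, so the main check sets the passages side by side.

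**1. Follow one event through the plan.** Take a mild rash on a neonate's chest on treatment day 3.

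| Step | Plan text | Result |
|---|---|---|
| Is it an adverse event? | Section 8: parents only | No |
| Is it a serious adverse event? | Section 8: neonates covered, but a serious outcome or important medical event is needed | No, if mild or moderate |
| Is it a non-serious adverse event? | Section 8: a subset of adverse events | No |
| Is it asked about? | Sections 5.B and 8: questions concern participants on treatment | No |
| Is it a neonatal data item? | Section 8 list | No |
| Could it be logged? | Section 8: other perceived adverse events | Yes, if volunteered or noticed |
| Is it compared by arm? | Section 9.C: Section 8 definitions | No |

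**2. Internal consistency.** The serious definition covers neonates and the general one does not. Serious events are therefore not a subset of adverse events as defined. It is also left unclear whether neonatal serious events belong in the Section 9.C comparison.

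**3. What collection could show.** Inputs: about 400 pairs (Section 4.A), so about 200 neonates per arm if balanced and treated as independent. Background rates of non-serious skin findings of 5% and 10%, and an excess of 1 to 3 percentage points, are assumptions, because the documents give none.

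- *Small counts.* Two reactions against none gives a two-sided Fisher p = 2 × C(200,2)/C(400,2) = 2 × 19,900/79,800 = 0.50.
- *Power.* Sum Bin(a; 200, p₀ + d) × Bin(b; 200, p₀) over all pairs (a, b) with two-sided Fisher p ≤ 0.05. With p₀ = 5%, power is about 5% at d = 1 point and 17% at d = 3 points. With p₀ = 10%, it is about 4% and 12%.
- *Precision.* With equal rates p in both arms, the 95% half-width for the difference is 1.96 × √(2p(1−p)/200). For p = 5% this is 1.96 × 0.0218 = 4.3 points. For p = 10% it is 1.96 × 0.0300 = 5.9 points.

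Collection would support a bounded descriptive statement. It would not give a sensitive test.

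**4. Timing.** Neonatal swabs are taken at baseline and then every 7 days (Section 4.D), so the first follow-up look falls after the 5-day course. Section 4.C.8 lists short-lived redness among the mild reactions to bathing. A weekly look alone could miss it, whereas the daily and Day 6 contacts would not leave that gap.

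**The case against.** **The choice looks deliberate.** The two definitions name different populations and the collection paragraph repeats the neonatal rule. Parents are the treated subjects, and secondary outcome 5 concerns reactions in them. This is probably so, but no section available to this review gives a reason for leaving out non-serious neonatal events. The subsection between 6.B and 6.D was not available, so I make no claim about it.

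**Recording is not barred.** A reader might infer that neonatal reactions are bound to be lost. The documents do not support that. The log accepts other perceived events, and Section 6.B sends expected and unexpected events to the DSMB and unexpected ones to the IRB, without limiting either to parents. The important-medical-event criterion would catch a severe reaction. This objection stands. What is missing is a definition, active questioning and a comparison by arm.

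**Exposure is inferred.** A reader might also take it as established that product reaches the infant. No section places skin-to-skin contact after cloth use or says that product transfers, and Section 6.A describes effects of the cloths without mentioning secondary contact. This stands too. Uncertainty about transfer is a reason to look, but it is not evidence of harm.

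**The comparison would be weak.** True for small excesses, as the power figures show. This limits what the data can prove, but counts by arm would still be informative to report.

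**Conclusion.** The gap is real and limited to safety reporting. Mild or moderate neonatal skin reactions are outside the adverse event definition, are not solicited, and are outside the planned comparison by arm. The adverse event and serious adverse event populations also need reconciling. This follows from the text of Sections 5.B, 8 and 9.C and needs no assumption. That it matters for infants rests on an inference about contact and transfer, which the documents make plausible but do not state.

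Two quantitative readings are tempting and not supported. One is to count missed reactions: the documents give no neonatal rate, and Section 6.A calls sensitization and allergy rare even for the product itself. The other is to claim that zero reactions in about 200 active-arm infants would cap the rate near 1.5%. That needs complete ascertainment and no background findings. At an assumed 5% background, the chance of seeing none is 0.95²⁰⁰, about 0.00004.

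The primary outcome, error rate, power and sample size are untouched. The change is worth making because it alters what the trial can report about infants at small cost.

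**What to change.** 1. **Section 8, definitions.** Make the adverse event and serious adverse event populations consistent by adding neonatal skin or contact reactions of any grade to the adverse event definition. State whether neonatal serious events enter the Section 9.C comparison.
2. **Sections 5.B and 8, collection.** Add one question about the infant's skin to the existing daily treatment contacts and the Day 6 contact. Record the answer on one CRF item, and complete the same item at the existing weekly neonatal swabs.
3. **Section 9.C, analysis.** Report neonatal reactions by arm, as counts with confidence intervals, alongside the Fisher's exact comparison. Say in advance that the result is descriptive.

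**Cost.** Protocol wording, one CRF item and one extra question, with no new visits. Background NICU skin findings will be recorded in both arms. The masked placebo arm gives the reference for these, but they add noise, and power for a small excess stays low.

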**NOTE: For the purposes of this trial, the following hospitalizations will not be considered SAEs:**

- Admissions as per protocol for a planned medical/surgical procedure;
- Routine health assessment requiring admission for baseline/trending of health status (e.g. post-partum complications, such as wound infection or bleeding);
- Medical/surgical admission for purposes other than remedying ill health state and was planned prior to entry into the study. Appropriate documentation is required in these cases;

- Admission encountered for another life circumstance that carries no bearing on health status and requires no medical/surgical intervention (e.g., lack of housing, economic inadequacy, care-giver respite, family circumstances, administrative).

**Non-Serious Adverse Event:** A non-serious adverse event is any adverse event not classified as serious. All non-serious AEs will be reported to the IRB on an annual basis with the continuing review.

**Adverse Event Grading:** The Division of AIDS Table of Grading Severity of Adult and Pediatric Adverse Experiences (DAIDS) Version 2 will be used to assess severity and provide the grade for each AE that is reported. The investigator will evaluate the severity of any adverse event not identified within the below criteria using the following definitions:

- **Mild (Grade 1)**- Mild symptoms causing no or minimal interference with usual social & functional activities with intervention not indicated
- **Moderate (Grade 2)**- Moderate symptoms causing greater than minimal interference with usual social & functional activities with intervention indicated
- **Severe (Grade 3)** - Severe symptoms causing inability to perform usual social & functional activities with intervention or hospitalization indicated
- **Potentially life threatening (Grade 4)** - symptoms causing inability to perform basic self-care functions with intervention indicated to prevent permanent impairment, persistent disability.
- **Death (Grade 5)**: Indicates death.

AEs graded as Grade 3 or higher which are possibly, probably, or definitely attributable to the use of the investigational drug will be recorded and monitored until the event has resolved to meet the definition of 'mild'.

All adverse events will be further evaluated for attribution as per the following:

- **Unrelated**: Adverse event is clearly not related to the investigational agent
- **Unlikely**: Adverse event is doubtfully related to the investigational agent
- **Possibly**: Adverse event is possibly related to the investigational agent
- **Probably**: Adverse event is probably related to the investigational agent
- **Definitely**: Adverse event is definitely related to the investigational agent

Participants who withdraw from the study, but who have AEs grade  $\geq$  "moderate" which are possibly, probably, or definitely attributable to the investigational drug will have AEs recorded and monitored until the event has resolved.

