## C. Enrollment

### 1. Patient Population and Setting

The Johns Hopkins Hospital (JHH) NICU is a 45 bed NICU in a quaternary care center that admits approximately 700 neonates per year. The Johns Hopkins Bayview Medical Center (Bayview) NICU is a 25-bed, level III unit with approximately 375 admissions per year. Neonates admitted to the JHH and Bayview NICUs and their parents or legal guardians will be screened for eligibility. **We will define parents as the biologic mother and the father. In the event that one of the parents is not available or does not visit the child in the NICU, we will ask the available parent to identify a primary visitor of the child in the NICU. Only 2 parents or one parent and one primary visitor will be enrolled for each neonate. In the protocol below, parents will refer to either a parent or a designated primary visitor.**

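### The SAE exemption for routine-assessment admissions gives post-partum complications as its only example, so a mother's unplanned admission that is serious only because of hospitalization loses SAE status

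*Combined protocol and SAP*

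**What the plan says.** **The rule.** Section 8 (Adverse Event Definitions) lists the outcomes that make an event serious and applies them to "any of the following outcomes in neonate and parent participants". The hospitalization criterion reads "Requires inpatient hospitalization or causes prolongation of existing hospitalization (see NOTE below for exceptions". The other criteria are death, threat to life, lasting disability, congenital anomaly and important medical event.

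**The exceptions.** The NOTE opens with "For the purposes of this trial, the following hospitalizations will not be considered SAEs" and has four bullets. The second exempts admissions for routine assessment, to establish or follow health status, and its only example is "post-partum complications, such as wound infection or bleeding". For comparison, the third begins "Medical/surgical admission for purposes other than remedying ill health state and was planned prior to entry into the study".

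**Who can be affected.** Section 4.C.1 states "We will define parents as the biologic mother and the father". Section 4.C.4 allows consent in the mother's room while she is still an inpatient after delivery.

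**What happens to the events.** Under Section 8, non-serious AEs go to the IRB once a year. Under Section 6.B, the DSMB receives safety data on expected and unexpected events, and unexpected events go to the IRB at once. Under Section 9.C, AEs are reported overall and by arm and compared with Fisher's exact test.

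**The concern.** The exempt category is an admission to assess or follow health status. The example is an admission because something has gone wrong. Site staff must either follow the category and ignore the example, or follow the example and exempt real complications. Two similar admissions could be classified differently at the two hospitals, or by two staff members at one of them.

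The event type is not remote from this trial. Every randomized family has at least one parent carrying *S. aureus* (Sections 4.C.2 and 4.C.6), many of the treated parents will have delivered recently, and the cloths are used on body areas that include the perineum (Section 4.B). A skin and nasal regimen directed at *S. aureus* could plausibly alter maternal wound infection. That is my inference; the documents do not state it. It is a reason not to settle the seriousness of such admissions in advance through an example in a list.

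At stake are the SAE label and the prompt reporting that would go with it. No endpoint, error rate, power figure or analysis set is involved.

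**Working it through.** No arithmetic applies. The check is to set the NOTE's bullets side by side and then apply the text to specific cases.

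**Step 1: the four exemptions compared.**

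| Bullet | What it exempts | Prior planning required? | Covers illness? |
|---|---|---|---|
| First | Protocol admissions for a planned procedure | Yes | No illness named |
| Second | Routine assessment or trending admissions | No | Yes: its only example is post-partum wound infection or bleeding |
| Third | Admissions not meant to remedy ill health | Yes, before study entry | Ruled out by its wording |
| Fourth | Social or administrative circumstances | No | Ruled out by its wording |

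The second bullet is the only one that names an illness, and it carries no planning condition that would confine it to elective stays.

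**Step 2: the bullet applied to three cases.**

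- *A mother admitted for a check, with no complication.* Exempt under the category, but the example does not describe her.
- *A mother admitted unexpectedly for a wound infection that is not life-threatening or disabling and is not judged an important medical event.* If the category governs, the admission is an SAE under the hospitalization criterion. If the example governs, it is not. The text gives both answers.
- *A mother with a life-threatening bleed.* An SAE on either reading, because the NOTE lifts only the hospitalization criterion.

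The defect therefore bites only in the second case, where admission is the sole serious feature.

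**Step 3: does another section settle that case?** In the text available to me (Section 6.C was not), nothing restores such an admission to SAE status under the hospitalization criterion.

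**Step 4: what remains visible after the label is lost?** A wound infection or bleed in a mother still fits the Section 8 definition of an AE. It is graded and attributed, and the investigator's fallback severity scale puts events for which hospitalization is indicated at Grade 3. It can enter the by-arm comparison in Section 9.C and belongs to the safety data for the DSMB in Section 6.B. What changes is the seriousness classification and, unless the event is treated as unexpected, the timing of the report to the IRB.

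**The case against.** The strongest reply is that the bullet can be read narrowly, as covering admissions to observe a known post-partum complication, or that the sponsor deliberately exempted common post-partum events. Either may be what was meant. Neither is what the bullet says. It is limited neither to observation of a known problem nor to planned stays, and a deliberate exemption for complications would not naturally sit under routine assessment. This reply does stand as a reason to let the sponsor state its intention.

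Three stronger readings are tempting, and the documents do not support them.

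- A reader might infer that the SAE definition and the NOTE contradict each other. They do not: the hospitalization criterion itself refers to the NOTE for exceptions. The mismatch lies inside one bullet.
- A reader might infer that the rule can remove every SAE of this type in mothers. It cannot, because the other seriousness criteria remain in force.
- A reader might infer that the DSMB would miss these events. The annual schedule concerns the IRB only; DSMB reporting in Section 6.B is not limited to SAEs. Section 9.C plans a by-arm comparison of AEs, which these events can still enter.

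It is also fair to say that the exemption applies to mothers in both masked arms, so the rule itself is not differential, and that the documents mention bleeding only in connection with swabbing and with epistaxis from the nasal ointment.

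**Conclusion.** The point holds in a limited form. The second bullet of the NOTE pairs a routine-assessment category with complications as its only example. As written, it takes SAE status from a mother's unplanned admission for post-partum wound infection or bleeding when hospitalization is the only serious feature.

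The size cannot be given: the documents contain no rate of maternal post-partum admission. The conclusion assumes that at least some staff will follow the example as written, and that some mothers will be readmitted for these complications while on study. The consequence is a less reliable SAE classification and possibly slower IRB reporting, not loss of the events. It is a minor point, worth correcting because correction is cheap.

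**What to change.** Reconcile the category with its example in the Section 8 NOTE. The simplest change is to delete the parenthetical, so that an unplanned post-partum admission falls under "Requires inpatient hospitalization or causes prolongation of existing hospitalization" like any other admission.

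If the sponsor does mean to exempt these admissions, list them as a separate, explicit exemption with a stated reason, and tabulate them by arm for the DSMB.

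The cost is a one-line protocol change and a few more SAE reports. Treatment, endpoints and sample size are untouched.
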